Title	Cervical cancer screening among HIV-infected women in Western Kenya: Evaluation of the safety, acceptability, and efficacy of an alternative ablation method for treatment of precancerous lesions
Study Description	The purpose of this study is to evaluate the safety, acceptability, and efficacy of Thermocoagulation for treatment of precancerous lesions among HIV-positive women in a screen-and-treat program in Western Kenya. Thermocoagulation is endorsed as an alternative to Cryotherapy for treatment of Visual Inspection with Acetic Acid (VIA) or Human Papillomavirus (HPV)-positive women by the 2018 Kenya national cancer guidelines. ³² Data primary from Western countries demonstrate similar efficacy for the treatment of precancerous lesions between Cryotherapy and Thermocoagulation. Data on safety, acceptability, and efficacy, particularly linked to gold-standard pathology, among HIV-positive women in low-resource settings are scarce. Given the demonstrated benefits over cryotherapy including increased portability and availability hence easier implementation, use of thermal coagulation for the treatment of precancerous lesions in low resource settings could significantly improve access to treatment compared with cryotherapy. This study seeks to fill a critical data gap by evaluating the efficacy of thermocoagulation among HIV-positive positive women using gold-standard biopsy for disease verification at baseline and follow-up, as indicated. We will also assess the safety and acceptability of this treatment modality among patients and providers.
Study Intervention	Thermocoagulation
Study population	HIV-infected women age 30 – 65 years old enrolled in care at the FACES- supported HIV clinics in Kisumu County in Kenya.

Objectives	
Primary Objective:
 
To evaluate the efficacy of thermal coagulation for the treatment of HIV-positive, HPV-positive women by assessing the rate of HPV persistence and CIN2/3 rate at 12 months after treatment.
 
Secondary Objectives:
 
To evaluate the safety of thermal coagulation for the treatment of abnormal cervical lesions within a screen-and-treat program among HIV-positive women in Western Kenya.
 
To evaluate patient satisfaction with thermal coagulation for the treatment of abnormal cervical lesions within a screen-and-treat program among HIV-positive women in Western Kenya.
 
Exploratory Objective:
 
To evaluate provider acceptability of thermal coagulation for the treatment of precancerous cervical lesion within a screen-and-treat program in Western Kenya.

Sample Size	
400 HIV-positive participants
 
We seek to enroll 400 participants in order to obtain sufficient numbers of women who have CIN2/3, our outcome of interest. Based on prior studies in this population, we anticipate approximately 35% of HPV-positive women (N ~ 140) will have biopsy-proven CIN2/3

List of Abbreviations

LMIC	Low- and middle-Income countries
VIA	Visual inspection with acetic acid
VAT	Visual assessment for treatment
HPV	Human papillomavirus
HR-HPV	High-risk human papillomavirus
HIV	Human Immunodeficiency Virus
WHO	World Health Organization
CIN2	Cervical intraepithelial neoplasia grade II
CIN2/3	Cervical intraepithelial neoplasia grade II or III
SCJ	Squamo-columnar junction
IARC	International Agency for Research on Cancer
JOOTRH	Jaramogi Oginga Odinga Teaching and Referral Hospital
FACES	Family AIDS Care and Education Services
LEEP	Loop excisional electrosurgical procedure
UCSF	University of California, San Francisco
KEMRI	Kenya Medical Research Institute
AE	Adverse Events
MOH	Ministry of Health
DNA	Deoxyribonucleic Acid
DSMC	Data and Safety Monitoring Committee
DSMP	Data and Safety Monitoring Plan
NCI	National Cancer Institute

Table of Contents

Protocol Signature Page	2
Protocol Signature Page – Participating Site	3
Abstract	4
List of Abbreviations.....	6
Table of Contents.....	7
1 Introduction.....	9
1.1 Abstract.....	9
1.2 Background.....	9
1.3 Literature Review	10
1.4 Study Rationale.....	11
1.5 Anticipated Application of Study Results	12
2 Study Objectives	12
2.1 Hypothesis	12
2.2 Primary Objective.....	12
2.3 Secondary Objectives	12
2.4 Exploratory Objective.....	13
3 Study Design	13

1.1 Abstract

Although cervical cancer is preventable, in 2018, an estimated 570,000 new cases will be diagnosed, 90 percent in low- and middle-income countries (LMICs).¹ Women infected with the Human Immunodeficiency Virus (HIV) are at increased risk of cervical cancer due to increased incidence and persistence of the human papillomavirus (HPV) infection, the causative agent.² Low-income countries have been unable to implement cytology-based screening programs used in high-income countries due to significant infrastructure and human resource requirements not feasible in these settings.³ In 2013, the World Health Organization (WHO) recommended cervical cancer screening using Visual Inspection with Acetic Acid (VIA) or HPV testing in LMICs, followed by immediate treatment with cryotherapy without histologic diagnosis.⁴ This screen-and-treat strategy decreases loss-to-follow-up, and is associated with a reduction in cervical intraepithelial neoplasia grade 2 and 3 (CIN2/3) and mortality from cervical cancer.^{5,8} However, impact on disease burden will not occur until women who screen positive are effectively linked to and receive treatment and appropriate follow-up. Currently, widespread implementation of cryotherapy programs has proven to be difficult given the need for bulky equipment that limits mobility in the field, and need for an ongoing supply of refrigerant gas which is expensive and of unrealizable quality.⁶ Recent data primarily among HIV-negative women suggests that thermal coagulation, an alternative treatment method, may be more feasible for implementation in LMICs, with similar efficacy compared to cryotherapy.^{6,7} If supported by more research, population-level implementation of thermal coagulation for the treatment of precancerous lesions within LMICs may result in increased access to treatment and hence secondary prevention of cervical cancer.

1.2 Background

Despite being a preventable disease through screening and vaccination, cervical cancer is a leading cause of death of women in Sub-Saharan Africa, where 90 percent of the 311,000 deaths in 2018 will occur.¹ In Kenya, cervical cancer accounts for 70-80% of cancers of the genital tract, and is the most common cause of cancer-related death for women, with an estimated 1700 yearly deaths.⁸ Cervical cancer is an AIDS-defining malignancy and women infected with the Human Immunodeficiency Virus (HIV) are at increased risk due to increased incidence and persistence of the human papillomavirus (HPV) infection, the causative agent.² Compared to HIV-negative women, women with HIV develop precancerous lesions at younger age and have faster progression to cervical cancer, making prevention efforts among this group particularly urgent.⁹ While access to the HPV vaccine may play the most significant role in cervical cancer control and elimination, access is currently limited in Sub-Saharan Africa, and its impact on cervical cancer will not be evident for at least twenty years.¹⁰ Therefore, effective cervical cancer screening remains a priority for cancer control in the current generation.

African countries have been unable to implement widespread cytology-based screening programs due to high infrastructure requirements and the need for multiple visits, leading to loss-to-follow-up.¹¹ In 2013, following significant evidence, the World Health Organization (WHO) recommended cervical cancer screening using Visual Inspection with Acetic Acid (VIA) or high-risk Human Papillomavirus (HR-HPV) testing in low resource settings, followed by immediate treatment with cryotherapy without histopathologic verification.⁴ This single-visit strategy decreases loss-to-follow-up in settings where women often overcome significant barriers to reach clinics and is associated with a reduction in CIN2/3 and mortality from cervical

cancer.⁴ Studies confirm that the benefit far outweighing the harms of overtreatment.⁴ However, while screen-and-treat with cryotherapy has demonstrated high cure rates – 88 percent for CIN1/2, and 77 percent for CIN3, and low rate of adverse events (2.1% with mild pain or cramping, 1.6% with malodorous excessive vaginal discharge, 0.7% with mild bleeding or spotting, and no severe adverse events noted)¹², there are significant barriers to widespread implementation, leading to a need for alternative treatment methods.^{6,13} Challenges associated with cryotherapy include bulky equipment limiting mobility, as well as the need for an ongoing supply of refrigerant gas which is expensive and of unrealizable quality in rural areas.⁶ An evaluation of 25 health facilities with cryotherapy services in Uganda showed that almost half of them were not operationally owing to lack of gas.⁶ In Malawi, over a 5-year period, only 43.3% of women who screened VIA-positive accessed treatment owing to challenges with delivering cryotherapy.¹⁴ This has led to a search of alternative, more easily implementable methods of treatment of cervical pre-cancer in low resource settings.

1.3 Literature Review

Thermal coagulation is an alternative ablative treatment method has increasingly been investigated for use in low resource settings. Thermocoagulation uses heat instead of cold to ablate cervical tissue - the superficial epithelium sloughs off after treatment, and the underlying stroma and glandular crypts are destroyed by desiccation.¹⁵ Similar to cryotherapy, studies support tolerability of thermocoagulation without the use of anesthesia, and the equipment supports self-sterilization.^{6,13,16} Compared to cryotherapy, thermal coagulation has several advantages for remote areas. Newer generation battery-powered devices are light and highly portable, weighing only 4.6 kilograms compared to 15-20 kilograms for each cryotherapy gas cylinder.⁶ Thermal coagulation also allows for faster treatment – a single application lasting 20 - 40 seconds, compared with the 3-min freeze, 5-min thaw, 3-min freeze cycle for cryotherapy, enabling treatment for more women.^{6,16} Widely accepted criteria for eligibility for treatment with thermocoagulation is similar to that for cryotherapy.⁶

Thermal coagulation has been used for treating CIN3 for 3-4 decades, primarily in the United Kingdom.⁶ In a systematic review of thirteen primarily European studies on the efficacy of thermal coagulation for treatment of CIN1-3 among 4569 patients, Dolman *et al.* report a 96% (95% CI 92 – 99%) cure rate for CIN1 and 95% (CI 92-98%) for CIN2/3 disease, comparable to published rates for cryotherapy.¹⁶

In the last few years, several small studies in LMIC have similarly reported comparable results with the use of thermal coagulation for the treatment of precancerous lesions. In Brazil, Naud *et al.* investigated the acceptability, safety and efficacy of thermocoagulation for the treatment of histologically proved CIN2-3.¹⁶ Among 52 women included in the study, 44 (85%) had no evidence of disease one year after thermocoagulation. The rate of no disease at follow-up was similar for women with CIN2 (17/20), 85% and those with CIN3 (27/32), 84%. At follow-up, disease status was evaluated by VIA and cytology, with colposcopy and biopsy as needed.¹⁷ Their study also reported no serious adverse effects following treatment with thermocoagulation. In Malawi, Campbell *et al.* report that 85% of approximately 300 VIA-positive women treated with thermocoagulation had negative VIA at 12-month follow-up, although they had no histological disease verification either at baseline or at follow-up.¹⁸ In Cameroon, Tran *et al.* evaluated the efficacy of thermocoagulation for treatment of biopsy-proven CIN2/3 among women age 30-49 years.¹³ Although limited by a small sample size, at 12-months follow-up, using cytology and biopsy to evaluate cure, 70.6% of women had no evidence of disease, comparable to the efficacy rates of cryotherapy within a similar population.^{6,19}

In a 2019 updated metanalysis of the efficacy of thermocoagulation for precancerous lesions including 7 studies from LMICs, Randall et al report a pooled estimate of 93.8% (95% CI 90.4 – 95.1).²⁰ The authors examined the effect of potential modifying factors on the cure rates for thermal ablation for treatment of biopsy-proven CIN2+. Studies restricted to countries in LMICs had a cure rate of 83.6% ((95% CI 78.2 – 88.2%)).²⁰

Data on safety and efficacy of thermocoagulation among HIV-positive women in low resources settings are limited. A 2016 Nigerian study among VIA-positive, HIV-positive women treated with thermocoagulation reported a cure rate of 81.7% (95% CI 74.7 – 88.6%), with cure defined as negative VIA at 12-month follow-up.²¹ In a metanalysis of LMIC studies including 155 HIV-positive women, 120 (84% - confidence interval not reported) were without evidence of dysplasia at follow-up, the majority assessed by VIA.²⁰

While limited, current data suggests that thermocoagulation is comparable to cryotherapy for treatment of precancerous lesions in HIV-positive women. The 2018 Kenya National Cancer Guidelines recommend the use of either Cryotherapy or Thermocoagulation for treatment of precancerous lesions among both HIV-positive and HIV-negative women.²² The WHO has convened a Guideline Development Group to review the evidence for thermocoagulation and is expected to make a recommendation.²⁰

1.4 Study Rationale

Despite significant progress in developing feasible and context-appropriate cervical cancer screening tools for low resource settings, impact on disease burden will not occur until all women who screen positive for precancerous cervical lesions are linked to treatment.⁶ Despite cryotherapy being WHO-recommended for use in screen-and-treat programs in LMICs, wide-scale implementation has proven challenging. Given the demonstrated benefits over cryotherapy, use of thermal coagulation for the treatment of precancerous lesions in low resource settings could significantly increase access to treatment compared with cryotherapy, potentially closing this important effectiveness gap in screening programs in low-resource settings.

Data on the safety, acceptability, and efficacy of thermocoagulation for treatment of precancerous lesions is limited, however, particularly among HIV-positive women who face disproportional burden of cervical cancer. From this study, we will provide crucial data on the safety, acceptability, and efficacy of thermocoagulation for treatment of CIN2/3 among HIV-positive women by supporting gold-standard biopsy verification at baseline and at 12-months follow-up after treatment. We will also evaluate provider acceptability of this new treatment method, a crucial aspect of widespread uptake. This data will inform national cervical cancer programs as well as inform policy and guideline development within the national government and the World Health Organization for this high-risk group of women in urgent need of prevention strategies.

We seek to investigate the safety, acceptability, and effectiveness of thermal coagulation for the treatment of biopsy-proven CIN2/3 among HIV-positive women in Western Kenya. We also seek to evaluate provider acceptability of thermocoagulation as a treatment method for precancerous lesions.

1.5 Anticipated Application of Study Results

The results from this study will provide crucial data on the safety, acceptability, and efficacy of thermocoagulation for treatment of CIN2/3 among HIV-positive women by supporting gold-standard biopsy verification at 12-months after treatment. If proven safe and efficacious, given the benefits over cryotherapy, there is potential for widespread adoption of thermal coagulation within screen-and-treat programs which may vastly improve access to treatment of precancerous lesions within Kenya and other LMICs, and support the goal of prevention, and elimination, of cervical cancer. This data will inform national cervical cancer programs as well as inform policy and guideline development within the national government and the World Health Organization for this high-risk group of women in urgent need of prevention strategies.

2 Study Objectives

2.1 Hypothesis

We hypothesize that the efficacy of thermal coagulation for the treatment of CIN2/3 among HIV-infected women will be similar to reported rates of cryotherapy among this population.

2.2 Primary Objective

To evaluate the efficacy of thermal coagulation for the treatment of HIV-positive, HPV-positive women by assessing rates of HPV persistence and CIN2/3 rate at 12 months after treatment

- Endpoints:
 - Proportion of women with no evidence of cervical dysplasia at 12-month follow-up based on colposcopy and biopsy.
 - Proportion of women with persistent HPV at 12-month follow-up

2.3 Secondary Objectives

To evaluate patient safety of thermal coagulation for the treatment of abnormal cervical lesions within a screen-and-treat program among HIV-positive women in Western Kenya.

- Endpoints:
 - Average pain score immediately after treatment
 - The rate of AEs reported at 4-6 week follow-up

To evaluate patient satisfaction with thermal coagulation for the treatment of abnormal cervical lesions within a screen-and-treat program among HIV-positive women in Western Kenya.

- Endpoint: Proportion of participants who answer 'yes' to satisfaction questions at 4-6 week follow-up.

2.4 Exploratory Objective

To evaluate provider acceptability of thermal coagulation for the treatment of precancerous cervical lesion within a screen-and-treat program in Western Kenya.

- Endpoint: Healthcare providers satisfaction scores on a validated Usability Likert Scale administered via a questionnaire.

3 Study Design

3.1 Characteristics

We will prospectively enroll four hundred HIV-positive women to undergo cervical cancer screening at FACES-supported MOH clinics in Kisumu County. After informed consent, clinical and demographic information will be collected, and participants will undergo cervical cancer screening using HPV testing. Women who previously screened positive for HPV (within the last 3 months) but have not undergone treatment will also be eligible for recruitment. Women with a positive HPV test will be evaluated for treatment with thermal coagulation, per WHO standards of ablative treatment. Per the WHO and Kenya Ministry of Health guidelines, women who will be candidates for thermal coagulation if the squamocolumnar junction is fully visualized, the cervical lesion covers less than 75% of the cervix, and there is no endocervical component or suspicion of cancer.⁸ Women who are not candidates for ablation will be referred to nearby a referral facility. All participants with a positive HPV test will undergo directed biopsy just prior to treatment for disease ascertainment but proceed to have same-day treatment, according to the WHO guidelines for screen & treat.

At 12-months after treatment, all participants treated at baseline will undergo repeat colposcopy, directed biopsy for those with cervical abnormalities or those with CIN2/3 at baseline, as well as provider collected HPV testing for persistence. Twenty-five percent of women with normal colposcopy will have a random biopsy at 6 or 12-O'Clock to confirm the absence of disease. Pain will be assessed immediately following treatment using a visual analog scale (VAS). The presence and severity of AEs will be assessed 4-6 weeks following treatment via a phone call, or in person visit, if warranted. Healthcare providers offering thermal ablation for the treatment of precancerous lesions will be surveyed at 4-6 week follow-up to evaluate provider acceptability and satisfaction with this treatment method.

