3.3 Sample Size and Power Calculation

The study sample size is calculated based on the primary objective.

We seek to enroll 400 participants in order to obtain sufficient numbers of women who have CIN2/3, our outcome of interest. Based on prior studies in this population, we anticipate approximately 35% of HPV-positive women (N ~ 140) will have biopsy-proven CIN2/3.²⁴ The study design is a non-inferiority trial using results from the only study using standard cryotherapy in a similar population¹⁹ to establish the non-inferiority boundary. We

will compare the efficacy rate in our study using thermocoagulation to the non-inferiority boundary established using the efficacy rate and lower 95% confidence bound from this cryotherapy treatment publication from a similar population.¹⁹

The efficacy results of cryotherapy in the De Vuyst paper were 77.2% (95% CI: 66.4-85.9%).¹⁹ Using 77.2% with a non-inferiority margin of 10% which is at the limit of the confidence bound and is closest to the null effect.²⁴ Using this margin, the new treatment method is hypothesized to be at least as good as cryotherapy. Based on this non-inferiority margin, a sample size of 140 women with CIN2/3 achieves 90% power in using a one-sided test with a significance level of 0.025. Based on this sample size, power of 90%, and significance of 0.025, the minimal detectable effect size (the actual difference between cryotherapy and thermocoagulation) is 0.0102.

We will leverage the robust HIV-care infrastructure at FACES in which patients are seen at every one to three months, and the presence of an established patient tracing system (including home visits) to reduce loss-to-follow-up. Assuming a 14% loss to follow-up, which would result in a sample size of 120, we are still be powered for our non-inferiority margin of 10% with a minimal detectable effect size of 0.0184, with 80% power and an alpha of 0.025. Sample size and non-inferiority calculations used NCSS PASS software and G-Power software.

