4.1 Eligibility Criteria

4.1.1 Inclusion Criteria

1. Age 30-65 years.
2. Enrolled in HIV care at FACES-supported clinics in Kisumu County.
3. Able to understand a written informed consent document, and willing to sign it.
4. Speaks a language that the consent form and data collection instruments are written in.

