7.1 Primary Objective

To evaluate the efficacy of thermal coagulation for the treatment of HIV-positive, HPV-positive women by assessing rates of HPV persistence and CIN2/3 at 12 months after treatment

Four hundred HIV-positive women with positive HPV testing will undergo colposcopy-directed biopsy for disease ascertainment prior to same-day treatment with thermal coagulation. At 12-months after treatment, all participants will undergo repeat HPV testing for persistence, and those who are HPV-positive will undergo repeat colposcopy, and biopsy as indicated for abnormal results, or random biopsy for 25% of those with normal colposcopy. We will define cure as a normal biopsy result or normal colposcopy among those who do not receive a biopsy.

Statistical Analysis: We will report the proportion of women with no evidence of cervical dysplasia at 12-months (primary outcome) follow-up, including 95% confidence intervals. We will extrapolate the rate of disease among those with normal colposcopy based on the rate of disease among the 25% in this group who will receive biopsy, and this will be incorporated in calculating persistence. We will perform a logistic regression to examine predictors of treatment success, using clinical and demographic variables as predictor variables. We will also report the rate of persistence of HPV at follow-up and compare with rates reported in the literature in this same population. We will compare efficacy rates for clearance of CIN2/3 to historical results following cryotherapy treatment in similar settings. A one-sample exact test will be used to compare the obtained efficacy proportion to that of historical controls.

We will leverage the robust infrastructure of the FACES in which patients are seen every one-to three months, and there is an established patient tracing system (including home visits) to reduce loss-to-follow-up. With a loss-to-follow-up rate of 10%, we will still be powered to answer this objective. Prior studies at this clinic have been able to achieve > 90% follow-up rate.³⁶ While limited by the lack of randomization to cryotherapy versus thermocoagulation, this study will provide pilot results that may enable a future randomized study evaluation of these two treatment methods.

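### The 400 is counted before HPV testing in 3.1 but as HPV-positive in 7.1 and in the arithmetic of 3.3; the 140 women with CIN2/3 need the second count and no referrals. The 12-month visit row in 8.7 also ends too early.

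*Combined protocol and SAP*

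**What the plan says.** **Counted at consent.** Section 3.1: "We will prospectively enroll four hundred HIV-positive women to undergo cervical cancer screening". Women consent first and are then HPV-tested; 5.1 gives the same order. The synopsis sample size is "400 HIV-positive participants". The inclusion criteria in 4.1.1 include "Enrolled in HIV care at FACES-supported clinics in Kisumu County" but no HPV result and no ablation criterion.

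**Counted as HPV-positive.** Section 7.1: "Four hundred HIV-positive women with positive HPV testing will undergo colposcopy-directed biopsy", followed by same-day treatment. Section 3.3: "we anticipate approximately 35% of HPV-positive women (N ~ 140) will have biopsy-proven CIN2/3".

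**A narrower group without a number.** Section 4.2 says that women who screen positive and are eligible for ablation form the study group.

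**Routes in and out.** In 3.1, "Women who previously screened positive for HPV (within the last 3 months) but have not undergone treatment will also be eligible for recruitment". Also in 3.1, "Women who are not candidates for ablation will be referred to nearby a referral facility"; 5.1 repeats the referral.

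**Losses.** Section 3.3: "Assuming a 14% loss to follow-up, which would result in a sample size of 120". Section 7.1 uses 10% instead. Neither deducts anything for referral.

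**Interim.** Section 8.5.5 sets it after one third of the planned women (133) are enrolled.

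**Calendar.** Section 8.7 marks enrolment in five quarters, April-June 2019 to April-June 2020. It marks 12-month visits in April-June and July-September 2020 only, and data analysis ends in July-September 2020. Sections 3.1 and 5.8 require the 12-month visit for all treated women.

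**The concern.** Four hundred is the only accrual target in the plan. A team that follows 3.1 and 4.1.1 could close accrual at 400 consents, some of them HPV-negative and some referred elsewhere, and hold fewer women with CIN2/3 than the non-inferiority comparison was sized for. Nothing in the plan tracks that number. Even if the 400 are all HPV-positive, a woman whose biopsy shows CIN2/3 but who was referred instead of ablated contributes nothing to the efficacy of thermocoagulation.

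The calendar is a separate matter. If visits stopped where the row stops, women treated in the later enrolment quarters would have no slot for the visit that yields the primary outcome.

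**Working it through.** **Inputs from the plan.** 400 women; 35% CIN2/3 among HPV-positive women; 14% loss (3.3) or 10% loss (7.1); reference rate 77.2%; margin 10 points, so the boundary is 67.2%; one-sided 0.025; true difference 0.0102 stated for n=140 (all 3.3); one-sample exact test (7.1).

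**Assumed, because the plan gives no figure.** HPV positivity h among the 400, and the share r of women with CIN2/3 who are referred.

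**1. The plan's own counts.** 400 × 0.35 = 140. With 14% loss, 140 × 0.86 = 120.4, the stated 120. With 10% loss, 140 × 0.90 = 126. The counts reproduce, but only with h = 100% and r = 0.

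**2. The 400 counted as in 3.1.** Women with CIN2/3 = 400 × h × 0.35, taking all of them as treated:

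| h (assumed) | before loss | after 14% | after 10% |
|---|---|---|---|
| 50% | 70 | 60 | 63 |
| 80% | 112 | 96 | 101 |
| 100% | 140 | 120 | 126 |

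The route for women already known to be HPV-positive has no cap, so h could in principle reach 100%.

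**3. The 400 all HPV-positive, some referred.** Analysable women before loss = 140 × (1 − r): r = 5% gives 133, 10% gives 126, 20% gives 112.

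**4. Exact power.** For each n, take the smallest count c with P(X ≥ c) ≤ 0.025 under X ~ Bin(n, 0.672). Power is P(X ≥ c) at a true rate of 0.772 (no difference) or 0.772 + 0.0102 = 0.7822:

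| n | c | true 0.772 | true 0.7822 |
|---|---|---|---|
| 140 | 106 | 0.703 | 0.796 |
| 133 | 101 | 0.679 | 0.774 |
| 126 | 96 | 0.653 | 0.749 |
| 112 | 86 | 0.593 | 0.691 |
| 70 | 56 | 0.347 | 0.425 |

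The stated 90% at n=140 is not reached in either column. That is a separate matter; here only the fall from the 140 row counts.

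**5. Interim.** 400 / 3 = 133, so the interim trigger takes on whichever meaning the 400 has.

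**6. Calendar.** Enrolment quarter plus 12 months:

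| enrolled | month 12 | in visit row |
|---|---|---|
| Apr-Jun 2019 | Apr-Jun 2020 | yes |
| Jul-Sep 2019 | Jul-Sep 2020 | yes |
| Oct-Dec 2019 | Oct-Dec 2020 | no |
| Jan-Mar 2020 | Jan-Mar 2021 | no, beyond the chart |
| Apr-Jun 2020 | Apr-Jun 2021 | no, beyond the chart |

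Three of the five enrolment quarters are not covered.

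**The case against.** The best defence is that the intended meaning can be recovered. Section 7.1 is explicit, the 140 in 3.3 works only on that meaning, the primary objective concerns HPV-positive women, and 4.2 confines the study group to women who screen positive and can be ablated. Against that stand one loosely worded sentence in 3.1 and unqualified wording in the synopsis and 4.1.1. This largely stands: 7.1 is probably what was meant, and the falls in step 2 belong to the reading that 7.1 contradicts. It does not remove the contradiction, because 3.1 and 4.1.1 are the sections that govern who is enrolled.

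It is also fair that 140 biopsy-proven cases do not depend on treatment, since all HPV-positive women are biopsied. Only the analysable number depends on it, and that is the number the efficacy test uses.

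A reader might infer that the trial will end with a few dozen women with CIN2/3 and almost no power. The documents do not support that: they give no positivity rate, and the known-positive route is uncapped. A reader might also infer from 8.7 that three fifths of the outcome data will be lost. That is not supported either. The chart is a planning table read from extracted text, its enrolment row also covers specimen collection, and 3.1 and 5.8 still require the visit for every treated woman.

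The interim is not a further defect. It only inherits the ambiguity; no stopping rule hangs on it, and adverse events are reviewed weekly (8.5.1).

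**Conclusion.** The inconsistency is certain; its size is not. The 140 requires all 400 to be HPV-positive, and all 140 are analysable only if every woman with CIN2/3 is eligible and treated. The plan states neither condition and makes no allowance for referral.

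On the likelier meaning, an assumed 5-20% referral among women with CIN2/3 leaves 133 to 112 before loss. Exact power then falls from 0.703 to between 0.679 and 0.593 with no true difference, or from 0.796 to between 0.774 and 0.691 at a difference of 0.0102. On the literal wording of 3.1 the fall could be larger (70 women at an assumed 50% positivity), but no document figure fixes it. The two loss rates, 14% and 10%, also disagree.

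The calendar mismatch needs no assumed rate, only the column positions in the table as extracted. It is a scheduling inconsistency, not a demonstrated loss of power. Both points should be fixed.

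**What to change.** Use one definition of the 400 in the synopsis, 3.1, 3.3, 4.1.1 and 7.1.

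- If it means HPV-positive, treated women, as 7.1 says, write that into 3.1, state how many consents are expected, and track treated women with biopsy-proven CIN2/3 against 140. Tracking is needed because the 35% is given for HPV-positive women, not for treated women.
- If it means women consented, restate the expected number with CIN2/3 and its power, with positivity, eligibility and one loss rate stated.

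In either case reconcile 14% with 10%, and count the interim 133 as treated women. In 8.7, extend the 12-month visit row to 12 months after the last treatment (about June 2021 if enrolment runs to June 2020) and place the final analysis after it.

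**Cost.** Mostly wording and one calendar row. The first option needs more than 400 consents: 400 / 0.80 = 500 at an assumed 80% positivity and 400 / 0.50 = 800 at 50%, before ineligibility. If 7.1 was always the intention, this is not a new burden. The second option means a lower stated number and power. Counting treated women makes the interim later.
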